6.4. Visit Windows

Due to the visit schedule defined in the protocol, two different schedules are applied when creating statistical outputs including tables, figures and listings. One is based on study day post dosing and the other one is based on patient age.

6.4.1. Study Day Based Visit Windows

For efficacy analysis, the time windows specified in [Table 4](#) describe how efficacy data will be assigned to protocol-specified time points, as displayed in the Schedule of Assessments in [SAP Section 3.5.1](#). All time points and corresponding time windows are defined based on Dosing Date.

If more than one efficacy observation for a specific assessment is included in a time window, the assessment closer to the nominal time will be used. If there are two efficacy observations equally distant to the nominal time, the latest one will be used in analyses. Any efficacy assessments occurring outside the analysis windows will be considered an assessment of an unscheduled visit.

Table 4: Study Day Based Visit Window

| Scheduled Visit | Nominal Days (Study Day) | Acceptable Analysis Window in Study Days (Min Day – Max Day) |
|--|--------------------------|--|
| Baseline | - | <1 |
| Month 1 | 30 | 1 to 44 |
| Month 2 | 60 | 45 to 74 |
| Month 3 | 90 | 75 to 104 |
| Month 4 | 120 | 105 to 134 |
| Month 5 | 150 | 135 to 164 |
| Month 6 | 180 | 165 to 194 |
| Month 7 | 210 | 195 to 224 |
| Month 8 | 240 | 225 to 254 |
| Month 9 | 270 | 255 to 284 |
| Month 10 | 300 | 285 to 314 |
| Month 11 | 330 | 315 to 344 |
| Month 12 | 360 | 345 to 374 |
| Month 13 | 390 | 375 to 404 |
| Month 14 | 420 | 405 to 434 |
| Month 15 | 450 | 435 to 464 |
| Month 16 | 480 | 465 to 494 |
| Month 17 | 510 | 495 to 539 |
| Month 18 | 540 | 540 to 569 |
| Month K | K*30 | K*30 to (K+1)*30-1 |
| Final Treatment Visit and 14 Months of Age Analysis Window | | 0 to ≤14 days after patient reaches 14 months of age (420-434 days of age) visit window; 0 to ≤14 days after patient reaches 18 months of age (540 days of age) visit window |

*Depending on age at time of dosing, patients will complete varying number of visits. The patient must complete a visit within 2 weeks after reaching 14 months of age; subsequent visits will be scheduled from that visit date. The patient must also complete the final study visit within 2 weeks after reaching 18 months of age.

Due to COVID-19 pandemic, a few patients may complete the final visit (18 months of age) months outside of protocol-defined visit window. Summary tables for efficacy analysis will be created based on the visits up to month 18 of age and any data collected after month 18 of age visit to the end of study visit will be grouped into “Month 19 of age and older. Data collected through the final visit will be presented in the listings. In case, multiple record falls within “Month 19 of age and older” visit then first record will be used for analysis.

Safety data, such as laboratory results, vital signs, ECGs, and physical exams will be assessed by date and study day. For lab data collected on an unscheduled visit, the protocol defined visit windows will be applied. For change from baseline analyses the value associated with the scheduled visit will be used. Due to the visit window (± 7 days) for Day 60 visit and Day 72

visit, there is an overlap when assigning data to these two visits. Data collected between Day 53 to Day 66 will be assigned to Day 60 visit. Data collected between Day 67 to Day 79 will be assigned to Day 72 visit. For summaries of shifts from baseline and potentially significant values, all post baseline values will be considered for these analyses. Baseline for safety measures will be defined as the latest value before Day 1.

6.4.2. Age Based Visit Window

Summary of efficacy endpoints, including CHOP-INTEND score and Bayley Scales will also be presented by Age (in months) which assigned as in Table 5. If more than one efficacy observation for a specific assessment is included in a time window, the assessment closer to the nominal time will be used. If there are two efficacy observations equally distant to the nominal time, the latest one will be used in analyses.

Table 5: Age Based Window in Months

| Age (Months) | Window for Days since birth |
|--------------|-----------------------------|
| < 1 month | 2 to 29 |
| 1 month | 30 to 59 |
| 2 months | 60 to 89 |
| 3 months | 90 to 119 |
| ... | ... |
| 15 months | 450 to 479 |
| 16 months | 480 to 509 |
| 17 months | 510 to 539 |
| 18 months | 540 to 569 |
| K months | $K*30$ to $(K+1)*30-1$ |

6.5. Data Cutoff Rule and Date

Due to COVID pandemic, a few patients delayed the scheduled end of study visits (month 18 of age visit). Analyses will be done after database lock.

6.6. Pooling of Centers

This is a multiple-center single dose treatment study. Given that the expected enrollment at most of sites is expected to be fewer than 5 patients, patients from all sites will be pooled together into a combined site in the analyses for the primary and secondary effectiveness endpoints. A site effect will be not examined because there will be too few patients within each center to provide an informative estimate of this effect.

6.7. Subgroups

Two subgroups based on age at dosing (study day 1) will be assessed in the selected analysis (developmental milestones and statistical modeling parts):

- Patients with age at dosing (study day 1) \leq 4 months (120 days)

- Patients with age at dosing (study day 1) > 4 months (120 days).

7. DEMOGRAPHIC, OTHER BASELINE CHARACTERISTICS AND MEDICATION

7.1. Patient Disposition and Withdrawals

Patient disposition will be presented for all patients, which will include the following:

- The number of patients screened
- The number (%) of screened patients who screen failed and the reasons for screen failure (inclusion/exclusion criteria, withdrew consent, and/or other) will be summarized. A listing of reason for screen failure will be provided for all patients who screen failed.
- The number (%) of patients in the safety population
- The number (%) of patients in the Efficacy Completer Population
- The number (%) of patients reach the 14 months of age for survival endpoint
- The number (%) of patients who completed the study, defined as all patients with a final scheduled visit conducted either remotely or at the study site
- The number (%) of patients who discontinued from the study and the associated reasons

For patients who discontinued due to AE, a separate summary table will be produced in order to detail the type of AE that resulted in the discontinuation (whether serious fatal, non-serious fatal, or non-fatal).

7.2. Demographic Data

The age of the patient at the time of gene therapy infusion will be summarized. The distribution of patients by sex will be presented. Patient demographics will be summarized using the Safety population.

Demographic data will be determined using the following calculations:

Age at Study day 1 = (Study day 1 visit date - date of birth + 1), expressed in days

Height/Length (in cm) = height (in inches) * 2.54

Weight (in kg) = weight (in lbs) * 0.4536

The following statistics regarding the patient's characteristics at birth will be summarized: gestational age (weeks), birth weight (kg), birth length (cm), and head circumference (cm).

The presence of significant medical conditions obtained from medical history will summarized. In particular, the following parameters will be summarized regarding symptoms and history of Spinal Muscular Atrophy: age at symptom onset (if applicable), baseline SMA symptoms (if applicable), family history of SMA, and number of siblings affected by SMA.

Patient baseline characteristics will be summarized on the Safety population by subgroup and overall.

7.3. Medical History and Concomitant Diseases

Medical history data will be summarized and presented using body systems and conditions/diagnoses as captured on the eCRF. The body systems will be presented in

alphabetical order and the conditions/diagnoses will be presented in alphabetical order within each body system. The number and percentage of patients in the safety analysis set with a particular condition/diagnosis will be summarized overall. Patients reporting more than one condition/diagnosis within a body system will be counted only once for that body system.

7.4. Prior and Concomitant Medications

Prior and concomitant medications will be summarized overall. A prior medication is defined as any medication taken prior to the date of the gene therapy infusion of study drug. A concomitant medication is defined as any medication that started prior to the date of the infusion of study drug and continued to be taken after the infusion of study drug or any medication that started on or after the date of the infusion of study drug. The number and percentage of patients in the safety analysis set taking prior or concomitant medications will be summarized by generic drug name based on the WHO Drug Dictionary.

7.4.1. Specific Medication Subgroups

To reduce the host immune response to the AAV-based therapy, patients will receive prophylactic prednisolone (approximately 1 mg/kg/day) 24 hours prior to the gene transfer and continuing for approximately 30 days. After 30 days of treatment, the dose of prednisolone can be tapered for patients whose ALT values, AST values, and T-cell response are ≤ 2 X ULN for ALT and AST, and < 100 SFC/ 10^6 PBMCs in accordance with the following treatment guideline:

- Weeks 5 and 6: 0.5 mg/kg/day
- Weeks 7 and 8: 0.25 mg/kg/day
- Week 9: prednisolone discontinued

The total number of days receiving prophylactic prednisolone and total cumulative dose of prophylactic prednisolone administered during the study (mg/kg, derived from the prednisolone log) will be computed for each patient. In case when other glucocorticosteroids were used, the doses should be converted into Prednisolone doses according to the conversion ratio, for example 4:1 for Hydrocortisone.

To compute total cumulative dose, the total dosing period is subdivided into dosing intervals represented by constant dose levels. On the day of a dosage change, the entire day is represented under the new dosing interval at the new dose.

For example, consider a patient who receives 1.0 mg/kg of prednisolone for Day 1 to Day 20, then on Day 20, dose is elevated to 2.0 mg/kg until Day 30, at which point it is tapered to 1.5 mg/kg. On Day 35, the dose is lowered to 1.0 mg/kg and continues until Day 40 when it is lowered further to 0.5 mg/kg until all prednisolone dosing stops on Day 45. For this patient,

$$\begin{aligned} \text{Total Cumulative Dose} &= (1.0 \text{ mg/kg} \times 19 \text{ days}) + \\ &\quad (2.0 \text{ mg/kg} \times 10 \text{ days}) + \\ &\quad (1.5 \text{ mg/kg} \times 5 \text{ days}) + \\ &\quad (1.0 \text{ mg/kg} \times 5 \text{ days}) + \\ &\quad (0.5 \text{ mg/kg} \times 6 \text{ days}) \\ &= 54.5 \text{ mg/kg} \end{aligned}$$

Exposure will be summarized for the Safety Analysis Set.

7.4.2. Other Therapies

Non-medication Therapies/Procedures will be defined as “Prior” and/or “Concomitant”. Prior Non-medication Therapies/Procedures are defined as therapies or procedures started prior to injection of AVXS-101. Concomitant Non-medication Therapies/Procedures are defined as therapies or procedures ongoing at time of injection of AVXS-101 or started after the injection. Non-medication Therapies/Procedures will not be summarized. A listing will be provided only.

8. EFFICACY

8.1. Primary Efficacy Endpoints and Analysis

8.1.1. Primary Efficacy Endpoint: Sitting Without Support up to 18 months of age

An independent expert reviewer will evaluate recorded videos of WHO MGRS assessments conducted at clinic visits. The reviewer will judge whether the video reveals evidence of the milestone achievement of functional independent sitting (Child sits alone without support for at least 10 seconds).

During the Screening visit, the physical therapist will complete an assessment of baseline milestone achievement, including functional independent sitting; this assessment must address all milestones/items noted in [Appendix 17.1](#) that are at or below the child's expected function for age. Items that are below the child's expected function for age that are not successfully achieved during the baseline evaluation should be repeated at subsequent visits until successfully performed.

The milestone of sitting without support will be assessed at every visit regardless of their initial status.

The number and percent of patients whom, through video evidence, exhibit the milestone achievement of sitting without support at any visit up to and including 18 months of age study visit will be summarized for the ITT population (and for identified subgroups). A one-sided Exact Binomial Test will be used to test the null hypothesis of $p=0.1\%$ at significance level of 0.025. Furthermore, the corresponding 97.5% confidence intervals will be estimated by the exact method for binomial proportions.

Descriptive statistics and statistical analyses for subgroups specified in [Section 6.7](#) will be provided to illustrate the consistency of the response rate across subgroups. If too few patients are in the subgroup to do an analysis, or an appropriate natural history or other appropriate comparator is not available, and a change from baseline analysis is not appropriate, descriptive statistics only will be provided.

This analysis will be repeated for the efficacy completers population.

An additional set of sensitivity analyses will be conducted to include patients who demonstrated the milestone of sitting without support, which occurred after but outside of the SAP-defined visit windows of the Month 18 of age visit due to COVID-19 disruptions.

8.2. Secondary Efficacy Endpoints and Analysis

8.2.1. Secondary Efficacy Endpoint: Avoidance of Death or Surrogate for Death (Permanent Ventilation)

The secondary efficacy endpoint is defined by avoidance of the combined endpoint of either (a) death or (b) permanent ventilation, defined as requirement of tracheostomy or ≥ 16 hours of respiratory assistance per day (includes non-invasive ventilatory support) continuously for ≥ 14 days in the absence of an acute reversible illness, excluding perioperative ventilation. Permanent ventilation, so defined, is considered a surrogate for death.

Non-invasive ventilatory support usage data (only available from Trilogy 100) will be extracted directly from each patient's device; the data will be downloaded from the device's SD card through software provided by the manufacturer and transferred as an external dataset.

An "acute reversible illness" is defined as any condition other than spinal muscular atrophy that results in increased medical intervention (i.e., increased requirement for external ventilator support; use of other concomitant meds as rescue) requirements and is expected to be reversible or improved following definitive intervention (i.e., surgery, antibiotics) or introduction of escalated supportive care, such as hospitalization (i.e., for upper respiratory infection, spontaneous fracture). The specific duration of the condition antecedent intervention shall not be considered in the definition of "acute". The date of "definitive intervention" shall be defined as the date of provision of a procedure (i.e., surgery, etc.) or medication (i.e., antibiotics) intended to cure or substantially improve the condition. For conditions, such as viral respiratory infections, for which supportive care is provided, the date of "definitive intervention" shall be considered the date of hospitalization or substantial escalation of care.

"Perioperative" use reflects any alteration of ventilator use related to a surgical or other medical procedure of any nature for which the participant received medications that could impair or interfere with respiratory function.

For a participant who develops an acute reversible illness and/or requires perioperative ventilator support, a recovery period not to exceed 21 days following the date of definitive intervention will be instituted. Following this recovery period, the condition will be considered sub-acute and the participant will become evaluable with regards to the surrogate survival endpoint (Requirement of ventilator support of ≥ 16 hours/day for greater than 14 days).

Example: Using this approach it would mean that on day 1, patient A receives definitive intervention for an acute reversible illness resulting in ventilator support for ≥ 16 hours/day. Days 1-21 will be provided to permit recovery from the acute reversible illness. On Day 22, the participant is no longer considered to have an acute illness. Should the participant continue to require ≥ 16 hours/day of ventilator support from day 22 to day 36, he or she shall be considered to meet the surrogate endpoint.

Statistical approach: The proportion surviving event-free to 14 months of age will be computed in the ITT population. Patients who terminate the study prior to reaching 14 months of age for any reason will be considered treatment failures (event).

As a comparator, in a natural history study of SMA Type 1 patients, [Finkel et al \(2014\)](#), 16 patients reached the combined endpoint of death or the need for a minimum of 16 hours/day of noninvasive ventilation support for a minimum of 14 continuous days by 14 month of age, one patient discontinued the study at age of month 4 and 6 patients event-free survived at age of 14 months.

The observed proportion surviving in the current study will be compared to the natural history data (5) of the matching cohort, using a 2-sided Fisher's Exact test, along with the corresponding 95% confidence intervals.

The number of patients survived in each subgroups specified in [Section 6.7](#) will be provided.

Time to death or permanent ventilation through 14 months of age is an additional sensitivity analysis. In case there is at least 1 patient who is event-free, but discontinue study prior to 14-months of age, a sensitivity analysis, based on the approach for time to event, will be carried out. In this analysis, time to event will be censored at 14 months of age or at the date of

discontinuation. The survival rate at 14 months of age will be estimated by Kaplan-Meier method, and survival curves for AVXS treated patients and the PNCr cohort will be compared using log-rank test at significance level of 0.05.

Additionally, the proportion of patients who experience each of the following events by 14 months of age will be summarized:

- Death
- Permanent ventilation

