12.1.7. Pulmonary Examinations

Pulmonary examinations will be performed by a pulmonologist (or appropriate individual as per standard institutional practice) as specified in the SoA ([Appendix 1](#)). Prior to trial entry, a pulmonologist (or appropriate individual as per standard institutional practice) will review and document ventilator usage in the 2 weeks prior to screening.

Patients may be fitted with non-invasive ventilator support at the discretion of the pulmonologist (or appropriate individual as per standard institutional practice) and/or Investigator. Non-invasive ventilator support equipment will be provided by AveXis, Inc. through a third-party vendor if not covered by the patient's insurance.

Should the patient require non-invasive ventilator support at any time during the trial, the usage should be recorded in eCRF. Patients requiring non-invasive ventilator support will be asked to bring the machine to each trial visit.

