3.8. Treatment Assignment and Blinding

This is an open-label study. All enrolled patients will receive AVXS-101.

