4.1.2. Secondary Efficacy Endpoints

The secondary efficacy endpoint is survival, defined as avoidance of either (a) death or (b) permanent ventilation through the 14 month of age visit. Permanent ventilation is defined by tracheostomy or requirement of ≥ 16 hours of respiratory assistance per day (via non-invasive ventilatory support) for ≥ 14 consecutive days in the absence of an acute reversible illness, excluding perioperative ventilation. Permanent ventilation, so defined, is considered a surrogate for death.

The respiratory assistance includes but is not limited to BiPAP machines, for example, Philips Trilogy 100 machine. Particularly, Trilogy 100 usage data will be saved in the SD card when patient uses the machine. Data in the SD card will be sent to AveXis by site during clinical visit. Daily usage information will be available when using DirectView software to extract the “compliance summary” from the raw data (.EDF files).

In addition, each site will be asked to verify whether permanent ventilation criteria were met for each patient. If a patient is reported to necessitate permanent ventilation, the date at which permanent ventilation was met will be reported by site.

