4.6.10. Non-invasive Ventilatory Support

Patients will be assessed by a pulmonologist at the time points specified in the schedule of assessments and may be fitted with a non-invasive positive pressure ventilator (e.g., Bilevel Positive Airway Pressure (BiPAP)) at the discretion of the pulmonologist and/or investigator. Non-invasive ventilatory support equipment may be provided by AveXis, Inc. through a third-party vendor (as necessary).

Each patient will be assessed by investigator whether permanent ventilation criteria has been met. If the patient meets the permanent ventilation criteria, the date of permanent ventilation met will be reported through [REDACTED]. Also, if [REDACTED] machine is used with SD card, the daily real hours of usage data will be sent to AveXis. Health-economics Endpoints

The analysis of healthcare resource utilization data may be performed for this study.

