6.2.4.2. Supportive (Secondary and exploratory) Efficacy Variables

The secondary efficacy endpoint, event-free survival, is defined as avoidance of any one of the following events up to 14 months of age, whichever occurred first:

- Death, *or*
- Tracheostomy, *or*
- Noninvasive Ventilatory support ≥ 16 -hour per day *and* continuously ≥ 14 days

Usage data for patients using non-invasive ventilatory support will be extracted directly from the device (e.g., Trilogy 100, Trilogy 200, ResMed Stellar) on an SD card, or USB stick and transferred as an external dataset, if available. Average daily use of non-invasive ventilatory support at baseline and monthly be summarized from data recorded on an SD card or USB stick and submitted in a format that is evaluable. If a patient did not have a device with the capability to record usage data at baseline and was using non-invasive ventilatory support prior to screening, the daily usage will be documented in the source documentation. As a secondary analysis, the amount of ventilation support will be categorized into None, $>0-\leq 12$ hours, $>12-\leq 16$ hours, ≥ 16 or permanent ventilation. At each of the above time points, the count and percent of patients in each ventilation support category will be presented.

Supportive (exploratory) efficacy variables are as follows:

- CHOP-INTEND summary score: This is assessed by evaluating the Baseline CHOP-INTEND scores compared to each scheduled visit time points (see [Table 4](#)), collected from patient's CRF. A summary score is obtained by summing the individual best-side scores.
- Achievement of Selected Threshold Scores on CHOP-INTEND: clinically relevant threshold scores were determined for categorizing CHOP-INTEND summary scores: ≥ 40 , ≥ 50 , ≥ 58 .
- Bayley Scales of Infant and Toddler Development[®] version 3: Two domains of motor and adaptive behavior will be assessed from patient's CRF at scheduled visits (see [Table 1](#)) with both raw and scaled scores provided.
- Age at which independent sitting (for 10 seconds) is first achieved.
- Ability to remain independent of ventilator support, defined as requiring no daily ventilator support/usage at 18 months of age.
- Ability to thrive as defined by maintaining the ability to swallow and to maintain weight ($>$ third percentile based on WHO CGRS without need of gastrostomy or other mechanical or non-oral nutritional support at 18 months of age)

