6.3. Handling Missing Data

All patients in the ITT analysis set will be included in the primary efficacy analysis for a given endpoint provided there are non-missing baseline values. If a patient misses a regularly scheduled visit, every attempt will be made to reschedule a visit within that visit window to obtain evaluations or tests.

For the primary endpoint (the ability to sit without support for 10 seconds at up to 18 months of age) collected during the study, only when a patient demonstrates the ability in a video recorded at a visit or at home and confirmed by a central reviewer, a “Yes/True” value will be reported in the MMI report. A missing value of the primary endpoint of a patient means the patient does not achieve the ability of the milestone. No imputation is necessary.

For secondary efficacy endpoint, only when a patient met the survival criteria, the date of death or permanent ventilation will be reported through [REDACTED]. Patients who terminate the study prior to reaching 14 months of age for any reason will be considered treatment failures (event). Patients who terminate the study after 14 months of age but are still event-free surviving at the time of termination will be censored.

The following strategies will be implemented for different efficacy endpoints

- Central reviewed developmental milestone. No imputation will be implemented
- CHOP-INTEND score. No sub item score will be imputed. If the missing total score is due to “Can not test (CNT)”, no imputation will be implemented. Otherwise, last observation carried forward (LOCF) will be applied to impute the missing values.
- Bayley Scales of Infant and Toddler Development. LOCF will be implemented to impute the missing values
- Swallowing, feeding support and ventilation support. No imputation will be implemented.

In addition, missing values for safety endpoints, including but not limited to AE, lab values, will not be imputed. For local lab, missing units or normal ranges will be reviewed by the medical team. If those missing information needs be imputed for selected lab tests, the imputed information will be captured in the Note to File (NTF). The following tables provides the most conservative way to impute the date of event, if a missing date observed and not able to be fixed on the source.

Table 2: Rules of Date Imputation: Pre-Dose Data

| Partial Missing Start or Stop Date | Imputed Start Date | Imputed Stop Date |
|--|--|-----------------------------------|

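### Permanent-ventilation events in the 14-month survival endpoint are declared by open-label sites and never checked against the ventilator logs being collected, and SAP 8.2.1 and 6.2.4.2 disagree on which devices supply logs

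*SAP*

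**What the plan says.** **Who declares the event.** SAP 3.8: "This is an open-label study. All enrolled patients will receive AVXS-101". SAP 4.1.2 says that "each site will be asked to verify whether permanent ventilation criteria were met for each patient" and that "the date at which permanent ventilation was met will be reported by site". SAP 4.6.10 adds: "Each patient will be assessed by investigator whether permanent ventilation criteria has been met". SAP 6.3 has the event enter the data as a reported date: "only when a patient met the survival criteria, the date of death or permanent ventilation will be reported through" (the name that follows is blacked out).

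**Which devices supply logs.** SAP 8.2.1, the endpoint section: "Non-invasive ventilatory support usage data (only available from Trilogy 100) will be extracted directly from each patient's device". SAP 6.2.4.2 gives a wider list: "e.g., Trilogy 100, Trilogy 200, ResMed Stellar) on an SD card, or USB stick and transferred as an external dataset, if available". Protocol 12.1.7 provides a further record: "Should the patient require non-invasive ventilator support at any time during the trial, the usage should be recorded in eCRF".

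**What the logs are used for.** The stated uses are descriptive: average daily use at baseline and monthly, with patients placed in hour categories (SAP 6.2.4.2), and hours per day between visits (SAP 10.11).

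**How the event is worded.** SAP 8.2.1 defines it with at least 14 days of support and excludes acute reversible illness and perioperative use. Later in the same section, the rule for the time after the 21-day recovery period asks for more than 14 days. SAP 6.2.4.2 lists the event without either exclusion.

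**The concern.** Survival is the only secondary endpoint and is formally tested once the primary succeeds. Its ventilation component needs two judgements: that support was required, and that no acute reversible illness explains it. Both are made by staff who know that the infant received gene therapy. The plan protects the primary endpoint from this problem by counting only milestones that an independent reviewer confirms (SAP 4.1.1). The survival endpoint has no comparable step, although an objective record of hours and days is being collected.

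If a site does not recognise or report a qualifying run, the infant remains a survivor unless death or early withdrawal makes the infant an event anyway. Nothing in the plan would bring the mismatch to light. The survival proportion would then be overstated, to an extent that cannot be assessed afterwards. The contradiction over devices matters because, under SAP 8.2.1, infants on other models would have no log to compare with the site report.

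**Working it through.** **1. Inputs.** Treated n=25, assumed survival 80% treated and 25% control (SAP 3.7). Control cohort 6/23 = 26.1% (SAP 5.6). Two-sided Fisher's exact test at 0.05, after success on the primary (SAP 3.11.2).

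**2. The plan's own figure.** Power was computed by exact enumeration of two independent binomials, rejecting when the Fisher p-value is at most 0.05. It is 97.9% for 25 against 25 and 97.6% for 25 against 23. Both stated claims are met: above 90% (SAP 3.7, Protocol 14.2) and at least 95% (Protocol synopsis).

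**3. Effect of one miscounted infant.** 1/25 = 4 percentage points.

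**4. Where the test could turn.** Fisher's test against 6/23:

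| Treated survivors | Proportion | p |
|---|---|---|
| 13/25 | 52% | 0.083 |
| 14/25 | 56% | 0.045 |
| 15/25 | 60% | 0.023 |
| 20/25 | 80% | 0.0004 |

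The smallest significant count is 14. From 20 survivors, significance is lost at 13, so 20 − 13 = 7 infants would have to change status.

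**5. A deliberately adverse illustration.** These assumptions are not in the documents: true treated survival p = 25%, equal to control; a share q of 30% to 70% of events are permanent ventilation; a fraction f of 10% to 50% of those are missed, in the treated group only. Apparent survival is p + (1 − p)qf, that is 0.25 + 0.75 × 0.3 × 0.1 = 27.3% up to 0.25 + 0.75 × 0.7 × 0.5 = 51.3%. The chance of a significant result favouring treatment rises from 1.6% to between 2.5% and 44%. This shows only the direction and the possible size if the drug did nothing for survival.

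**6. Would the planned tables reveal a mismatch?** Not reliably. Over a 30-day month (the SAP's convention), 14 days at 16 hours and none on the other days average 14 × 16 / 30 = 7.5 hours a day. That falls in the category above 0 and up to 12 hours, although the run meets the hours-and-days rule.

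**7. Is the run rule the same throughout?** No. The SAP 8.2.1 example continues support from day 22 to day 36, which is 36 − 22 + 1 = 15 days. A run of exactly 14 days after recovery (day 22 to day 35) meets the definition at the head of SAP 8.2.1 and the wording of Protocol 14.1.1.1.2. It fails the later SAP 8.2.1 sentence.

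**The case against.** Much of the case on the other side stands.

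- **The site is not named as sole arbiter.** A reader might infer that the site report overrides the log. The SAP does not say so. Section 4.1.2 describes the log data first and adds site verification to it, 8.2.1 places log extraction inside the endpoint section, and 6.3 does not say who reports the date. The deciding source is unspecified.
- **The one-model limit does not itself produce a miscounted survivor.** An infant with no log cannot have a log that meets the definition. The gap is the missing reconciliation rule; the limit only narrows what could be reconciled.
- **Mixed devices are possible, not established.** Protocol 12.1.7 has the sponsor supply equipment where insurance does not, with 12–16 sites in eight countries planned. SAP 10.9 says without condition that the sponsor will provide it.
- **A log shows use, not need.** It cannot show acute illness or perioperative use, so an infant with a long run may correctly be a survivor. Counting every log-derived run as an event in the main analysis would replace requirement with use.
- **The comparator is not a pure hours count.** SAP 5.6 and 8.2.1 describe the natural history events as a need for 16 hours a day, which is also a judgement.
- **Errors do not all raise survival.** A late report that arrives before lock does no harm. An infant who dies or leaves before 14 months is already an event (SAP 6.3). A site may also over-report.
- **The eCRF may not help.** Protocol 12.1.7 asks for usage, without requiring daily entries.

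What remains is that no rule compares the two sources or resolves a difference between them, and that the SAP contradicts itself on devices and on the event wording.

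**Conclusion.** The point holds as a cheap improvement. The plan collects usage data that could verify a component of a tested endpoint, gives those data only descriptive uses, and leaves open-label sites to declare the event with no stated way of settling a disagreement. An infant whose log meets the full definition, exclusions included, could be counted as a 14-month survivor.

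The size is 4 percentage points per infant, assuming 25 treated infants. The significance test depends on a single infant only near 14/25 survivors. A reader might infer that the survival test is unsafe; at the planned 80% it is not, since seven reclassifications would be needed. Phase 1 also points away from that margin: Protocol 5.4 reports all 15 patients alive and free of permanent ventilation at 24 months. The benefit of a change is therefore mainly a survival estimate that can be audited. The documents give no basis for saying how often a log and a site report would differ.

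**What to change.** Before database lock, amend the SAP as follows.

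1. In 8.2.1, delete the parenthesis that limits usage data to Trilogy 100, and use logs from every device type in 6.2.4.2. Use eCRF or source usage only where day-level entries exist.
2. Program a search for runs of at least 14 consecutive days at 16 hours a day or more. Apply the existing acute-illness, perioperative and 21-day rules, and query every disagreement with the site report.
3. Base the main analysis on event status after those queries. Add a sensitivity analysis that counts every log-derived event.
4. Reconcile the two day counts within 8.2.1, and the list in 6.2.4.2 that omits the exclusions with the definition in 8.2.1.

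The cost is SAP wording, some programming and a number of site queries, with no new patient procedures. Because a log shows use rather than need, some queries will confirm the site's view. The survival estimate may come out slightly lower.
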